- **Neuropsychiatric Inventory (NPI & NPI-Distress):** The NPI¹⁰⁴ is a 40-item tool developed to assess behavioral abnormalities in individuals with dementia. Since its development, the NPI has been used in TBI populations to assess neurobehavioral dysfunction.^{23,43,50} It is a fully structured observer interview that specifies verbatim the questions to be asked. The observer indicates if a specific behavior has been present during the past month or specified time period and if this represents a change from premorbid functioning. The most problematic behavior detected by the sub-questions is then used to grade the frequency and severity: behavior severity (1 = mild, 2 = moderate, 3 = severe) and frequency (1 = occasionally, less than once per week; 2 = often, about once per week; 3 = frequently, several times per week, but less than every day; 4 = very frequently, once or more per day or continuously) and the product (severity x frequency) is calculated (range 0-12). The NPI also assesses the caregiver’s distress over the behaviors on a 6-point scale: 0 (no distress), 1 (minimal), 2 (mild), 3 (moderate), 4 (moderately severe), and 5 (very severe or extreme).

For the present study, we will use the NPI Irritability and Aggression domains as outcome measures. The Irritability domain includes: bad temper, rapid mood changes, sudden anger, impatience, crankiness, argumentativeness. The Aggression domain includes: getting upset, resisting activities, stubborn, uncooperative, hard to handle, shouts, curses angrily, slams doors, kicks furniture, throws things, hurts or hits others.

The NPI has established content and concurrent validity, as well as inter-rater (approximately 95% for both frequency and severity), test-retest (0.79 for frequency and 0.86 for severity), and internal consistency reliability (Cronbach’s alpha of 0.88 for both).¹⁰⁴ The NPI-Distress has established content and concurrent validity, and inter-rater (0.96), test-retest (0.92), and internal consistency reliability.¹⁰⁵

Few scales exist to specifically assess irritability in neurologic disorders. Other available measures ask only about the presence or frequency of irritability. Only the NPI assesses the distress caused by the irritability. This multifaceted assessment of the problem makes the NPI ideal for the study of irritability in TBI, and specifically in this medication trial.

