instructed to reduce the dose to the next lowest tolerable dose or the study drug will be discontinued (depending on symptom severity). If intolerable symptoms have not subsided within 4 days or clinically appropriate time frame, the drug will be discontinued or titrated down further, whichever is most appropriate in the investigator’s judgment. In the extremely unlikely event that the subject experiences signs or symptoms of life-threatening side effects, the study treatment will be withdrawn. The participant will be reassessed at the next visit or called for possible dose increase if symptoms have resolved or no longer appear to be related to study drug. Regardless of dose, testing will proceed according to the delineated schedule through to Day 91.

If the dose had been adjusted downward due to AE then at the scheduled Study Visit the dose would either stay the same as currently tolerated or advanced to the next dosing increment depending on the participant’s clinical picture and time of the prior change in dose. If a participant is still having trouble adjusting to the last dose escalation, we will wait an additional week before trying to escalate to the next dose.

Blinding Procedure: The placebo pills will be identical in appearance, smell, and taste. Participants, family members, treating staff, physicians, RA/data collector and investigators will be blinded to group assignment until after the final study analyses. The dispensing pharmacist will be the only person unblinded.

Drug Identification in Emergency: The blind will not be broken until the end of the study unless medical treatment decisions depend on knowing the group assignment. Procedures for unblinding are outlined in the Manual of Procedures. An unblinding form prompts the clinician to think through all of the reasons for unblinding to ensure that unblinding is indeed necessary.

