• Review medication instructions and dosing
• Advance drug dose (60 mg/day) unless prevented by adverse event or improved $\geq 80\%$ on NPI-I
• Remind of next study visit
• Instruct to bring in any remaining study medication to the next study visit
Calls 9, 10, and 11 (Days 70, 77, and 84 +/- 3 days):
• Inquire about number of pills taken and any problems encountered, record adverse events, record any change in concomitant medications
Visit 4 (Day 91- 3 or + 7 days): Final Outcome Visit in-person or via telephone
• Record number of remaining pills
• Collect unused medication
• Record any change in concomitant medications
• Record adverse events
• Vital signs*****
• Administer assessment measures to observer about individual with TBI: NPI & NPI-D Irritability & Agitation Domains, GIC, SASNOS, AIIM, Summary Questionnaire
• Administer assessment measures to participant about self: NPI & NPI-D Irritability & Agitation Domains, TBI QOL Anger, AIIM, PHQ-9, GAD-7, GIC, WAI-SR, Summary Questionnaire
• Record WAI-SR
• Record Clinical Global Impressions
• Ask if they think they have been receiving placebo or BUSP
• Encourage subject to make clinical appointment with rehabilitation physician for routine care and continued management, including addressing irritability as needed.
• Give subject 1-week supply of tapering dose BUSP and 1 month supply of open-label BUSP
Call 12 (Day 131 +/- 7 days): Final Safety Call
• Inquire about any problems encountered during taper and open label and record adverse events
• Complete Study Completion Form

Summary of Measures and Who Will Respond:

Measure	Buspirone Study	Measurement Study	Observer	Participant	Clinician	Research Assistant
NPI & NPI-D Aggression	X	X (observer)	X	X		
NPI & NPI-D Irritability	X	X (observer)	X	X		
SASNOS	X	X	X			
TBI-Quality of Life-Anger	X	X		X		
Personal Health Questionnaire (PHQ-9)	X			X		
Generalized Anxiety Disorder (GAD-7)	X			X		
Aggression & Irritability Impact Measure (AIIM)	X	X	X	X		
PTSD Checklist Civilian (PCL-C)	X			X		
Glasgow Outcome Scale Extended (GOS-E)	X			X (or best source)		
Clinical Global Impressions (CGI)	X				X	
Global Impression of Change (GIC)	X		X	X		
Working Alliance Inventory-Short Revised (WAI-SR)	X	X		X		X

Schedule of Events:

Procedure	Baseline Visit 1	Calls***	Visit 2 Day 35 (-3 or + 7)	Visit 3 Day 63 (+/- 3 days)	Visit 4 Day 91 (-3 or + 7)
Informed consent	X				
Screen for eligibility criteria	X				
Past medical history	X				
Vital signs *****	X		X	X	X

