Side Effects and Adverse Events: All AEs encountered during the study will be recorded beginning at the time the informed consent form is signed. Participants will be encouraged to report each AE, and will be queried about AEs with each contact. All clinically significant changes in health status will be recorded and followed, including the date and time of onset, severity, relationship to study medication, the date of resolution (or the fact that the event is still continuing), the action taken, and the outcome. The PI will categorize each AE according to its severity (mild, moderate, severe) and suspected relationship to the study treatment. AEs not resolved at the completion of a protocol are followed until resolution or for duration as deemed appropriate by the Data Safety Monitoring Board (DSMB). Serious adverse events (SAEs) will be reported to the local IRB within 24 hours of the project staff becoming aware of the event. A study pager and call schedule will be maintained to assure timely communication.

Clinical and Safety Monitoring: The PI, Project Manager, Clinical Monitor, and DSMB, all with the training and experience to oversee the study conduct, will monitor the study in accordance with Good Clinical Practices. A Clinical Monitor from the Indiana CTSI will review record accuracy and completeness, check source documents, and evaluate study data (drug accountability, communication, and written records). The DSMB will monitor the study for purposes of safety and integrity, which will include review of AEs, SAEs, protocol deviations and violations, and data quality reports. A Manual of Procedure will be developed that specifies our procedures that guide dose adjustment and management of AEs, SAEs, and suicidal ideation.

7.1/2 STUDY WITHDRAWAL/DISCONTINUATION

Subject Withdrawal: Subjects may discontinue or withdraw from the study for any of the following reasons: (1) subject's request, (2) adverse event requiring treatment discontinuation, (3) investigator deems necessary. If a subject withdraws or is discontinued for any reason, they will be asked if they will return to the site as soon as possible where all Final Visit assessments will be conducted as is necessary for an intent-to-treat analysis.

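### The protocol does not separate stopping study drug from leaving assessment, so the Day 91 primary outcome may go uncollected in participants taken off drug for an adverse event

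*Combined protocol and SAP*

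**What the plan says.** Section 5.1, Dosing Adjustments, sets out what happens when adverse events are intolerable. Participants are "instructed to reduce the dose to the next lowest tolerable dose or the study drug will be discontinued", depending on severity, and for life-threatening effects "the study treatment will be withdrawn". The same paragraph ends: "Regardless of dose, testing will proceed according to the delineated schedule through to Day 91".

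Section 7.1/2, Subject Withdrawal, lists three reasons for which a subject may discontinue or withdraw from the study. The second is "adverse event requiring treatment discontinuation". Of anyone who withdraws or is discontinued, whatever the reason, it says "they will be asked if they will return to the site as soon as possible where all Final Visit assessments will be conducted", and it gives the needs of the intention-to-treat analysis as the justification. It mentions no later Day 91 assessment.

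Three other places bear on this:

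- Sections 2.1 and 8.1 define the primary outcome as a fall of at least 3 points in the observer-rated NPI Irritability score from baseline to Day 91, analysed by intention to treat.
- The Study Sequence in section 5.1 describes Visit 4 as a "Final Outcome Visit in-person or via telephone", with a window of 3 days before to 7 days after Day 91.
- The NPI description in section 5.1 gives the recall frame: "The observer indicates if a specific behavior has been present during the past month or specified time period".

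**The concern.** One event, study drug stopped for an adverse event, falls under both sections, and they point to different data collection. Under section 5.1 the participant is rated at the remaining scheduled visits, including Day 91. Under section 7.1/2 the same participant can be treated as leaving the study and be asked for one set of Final Visit assessments straight away.

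An early rating is not the outcome that the intention-to-treat analysis needs, which is response at Day 91. It follows less time in the study and possibly fewer dose steps. If the past-month recall frame is used, a rating before about Day 30 also covers some time before the first dose.

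The loss is avoidable. The primary score comes from the observer, and Visit 4 can be done by telephone. Yet section 7.1/2 asks those who leave to come to the site, which is more than is asked of those who complete.

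If stopping for adverse events is more common in one arm, the off-schedule or absent scores will be unbalanced. Day 91 scores that were never collected cannot be recovered at the analysis stage.

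**Working it through.** **1. The two rules side by side**

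| | Section 5.1, Dosing Adjustments | Section 7.1/2, Subject Withdrawal |
|---|---|---|
| Trigger | Intolerable or life-threatening adverse event; drug reduced, stopped or withdrawn | Adverse event requiring that treatment stop, among other reasons |
| Status | Still being tested | May discontinue or withdraw from the study |
| Next assessment | As scheduled, to Day 91 | Final Visit set as soon as possible |
| Mode | In person or telephone (Visits 2 to 4) | Return to the site |
| Day 91 rating | Yes | Neither required nor cancelled |

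The Visit 4 window runs from 91 − 3 = Day 88 to 91 + 7 = Day 98. A Final Visit held before Day 88 is outside it. Section 8.1 does not say whether such a score stands in for Day 91, and it has no missing-data rule.

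**2. The plan's own sample size**

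Inputs from section 8.1: 40% against 80%, chi-square test, alpha 0.05, power 90%. Two-sided testing is assumed because the section does not say.

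- Normal approximation, no continuity correction: n = [1.960 × √(2 × 0.6 × 0.4) + 1.282 × √(0.4 × 0.6 + 0.8 × 0.2)]² / 0.4² = 29.4, so 30 per arm. With continuity correction: 35.
- Fisher's exact test by enumeration: 90.1% power at 33 per arm, 88.7% at 32. This reproduces the planned 33.
- Allowance for loss: 33 / 0.90 = 36.7, so 37 per arm, as planned.

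None of these figures is in dispute.

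**3. How many participants**

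The documents give no rate of stopping for adverse events. As an assumed range, take the 5% drop-out in the earlier studies (0.05 × 37 = 1.9, about 2) and the planned 10% loss (0.10 × 37 = 3.7, about 4). Both describe loss in general.

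**4. Power at 37 per arm**

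Exact enumeration of the uncorrected two-sided chi-square test. Everyone who stays on drug responds at the planned 80% (buspirone) or 40% (placebo). Unless stated, stops are in the buspirone arm only.

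| Scenario | Buspirone response | Placebo response | Power |
|---|---|---|---|
| No stops | 80% | 40% | 95.1% |
| Four stops, scores simply missing (33 against 37) | 80% | 40% | 94.5% |
| Two stops, scored as non-response | 0.80 × 35/37 = 75.7% | 40% | 88.5% |
| Four stops, scored as non-response | 0.80 × 33/37 = 71.4% | 40% | 78.1% |
| Four stops in each arm, scored as non-response | 71.4% | 0.40 × 33/37 = 35.7% | 87.9% |
| Two stops, all followed to Day 91, stoppers respond at 40% | (0.80 × 35 + 0.40 × 2)/37 = 77.8% | 40% | 92.3% |
| Four stops, all followed to Day 91, stoppers respond at 40% | (0.80 × 33 + 0.40 × 4)/37 = 75.7% | 40% | 88.5% |

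**5. What the table shows**

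The fair comparator for lost Day 91 data is the follow-up rows, because collecting Day 91 scores does not restore an 80% response in people who have stopped the drug. Against those rows, scoring stoppers as non-responders costs 88.5 − 78.1 = 10.4 points with four stops and 92.3 − 88.5 = 3.8 points with two.

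Power is also not the best measure. With four stops followed to Day 91, the difference is 75.7 − 40 = 35.7 points. Leaving the four out gives 80 − 40 = 40 points, which is 4.3 too high. Scoring them as non-responders gives 71.4 − 40 = 31.4 points, which is 4.3 too low. Under the same assumptions, the direction of the error depends entirely on how the missing or early score is handled, and section 8.1 does not say how.

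**The case against.** The strongest reply is that the two sections can be read together: section 5.1 for those who stop drug and stay, section 7.1/2 for those who leave. Section 7.1/2 is permissive, since subjects may withdraw and are asked whether they will return, and it does not cancel Day 91. Dose-adjustment and adverse-event detail is also referred to a Manual of Procedures that is not part of these documents. Much of this stands. A reader might infer that the sections give opposite rules that no site could follow together, or that the Day 91 outcome is necessarily lost. The text supports neither. What remains is that the reconciling distinction is not written down, and that section 7.1/2 makes stopping treatment for an adverse event itself a ground for leaving.

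A reader might also infer a power loss from about 95% to 78%. That needs early visits to count as non-response, a rule found nowhere in the documents, and four adverse-event stops in one arm with none in the other. It also compares against a trial in which nobody stops.

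Nor do the documents show that early scores push the buspirone arm towards non-response. A rating soon after stopping may reflect behaviour while on drug, whereas Day 91 would reflect behaviour off it. The half-life given in section 2.0 is 2 to 3 hours. The nausea figures there (8% against 1%) are event frequencies, not discontinuation rates; they make unequal stopping plausible but do not measure it. Section 5.1 expects few side effects, usually diminishing within 3 to 4 days. The recall argument is conditional too, because the NPI wording allows a specified period other than the past month.

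**Conclusion.** The point holds as an undrawn distinction with an avoidable cost. For a participant whose drug is stopped for an adverse event, the protocol supports both continued testing to Day 91 and an early on-site Final Visit. If a site follows the second, the primary outcome may not be collected in someone who could still provide it by telephone.

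The effect on power is small if the scores are simply missing: 94.5% against 95.1% with four missing in one arm. The main risk is bias in the intention-to-treat comparison if stopping differs between arms, in a direction that the documents do not settle. In the four-stop illustration it is about 4 percentage points either way. These sizes rest on an assumed 2 to 4 stops, two-sided testing, the planned 80% and 40% response rates and, in the follow-up rows, an assumed 40% response after stopping. This is a worthwhile, inexpensive correction and does not threaten the design.

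**What to change.** Reconcile the two sections by adding to section 7.1/2:

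- A participant who stops study drug but does not withdraw consent stays on the section 5.1 assessment schedule. Any remaining ratings at Days 35, 63 and 91 are obtained in person or by telephone, including the observer NPI.
- The early Final Visit is used only for those who withdraw from further assessment. A later observer rating is sought only where both participant and observer still consent.
- The date drug was stopped is recorded.

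Section 8.1 should then state which measurement enters the Day 91 responder analysis and how a missing one is handled.

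The cost is a short wording change and a few extra telephone contacts, for perhaps 2 to 4 participants per arm on the assumed range. The change concerns data collection only and takes no position on when study drug should be stopped.

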8.1 STATISTICAL CONSIDERATIONS

General Considerations: Statistical analyses for this study will be the responsibility of the study statistician working through the Department of Biostatistics. Safety and efficacy analyses will be conducted on all evaluable patients. Parameter estimates and relevant summary statistics will be reported where appropriate. For continuous variables, summary statistics will include number of patients, mean, median, standard deviation, minimum and maximum. Categorical variables will be summarized using number of patients, frequency, and percentages. Additional exploratory analyses of the data will be conducted as deemed appropriate. Changes from this analysis plan will not require an amendment to the protocol unless it changes a significant feature in the protocol. The statistical analysis methods are detailed below. Standard statistical methods will be employed. Descriptive statistics, including means and standard deviations, or counts and percentages will be calculated. As a majority of the outcome variables are measured on the ordinal (Likert) scale, nonparametric statistical tests will be employed. The SAS® software, version 9.3,¹⁶⁶ will be used. A p-value of less than 0.05 will be considered statistically significant unless otherwise noted. Analysis plans specific to each hypothesis are further discussed below.

Analysis Sets: The definitions of the study populations are listed below:

Population	Definition
Intention-to-Treat	All patients who meet the eligibility criteria and are registered for the study irrespective of their compliance to the planned course of treatment.
Per Protocol Set	All patients who complied with the protocol sufficiently to ensure that these data would be likely to exhibit the effects of treatment, according to the underlying scientific model. Compliance covers such considerations as exposure to treatment, availability of measurements and absence of major protocol violations.

Population	Definition
Safety	All patients receiving at least one dose of study drug are included in the analysis of safety, unless otherwise noted.

Participant Characteristics: Participant demographics and baseline characteristics will be listed and summarized for the Intent-to-Treat population, including age, gender, ethnicity, height, weight and medical history.

Demographic and baseline measurements will be compared between the two groups. Variables measured on an interval scale (e.g., age) will be compared between the two groups with a Student's t-test. Variables that are not normally distributed will be tested with the Wilcoxon rank sum test. The chi-square test or Fisher's exact test will be employed for variables measured on the nominal scale (e.g., gender).

Concomitant Medications: Concomitant medications will be summarized.

Participant Disposition: Disposition will be tabulated showing the number of those entered and discontinued for any reason. Reasons for discontinuation will be listed and summarized.

Compliance: Number of subjects who are compliant with respect to pill taking (defined as $\geq 75\%$ of prescribed study medication consumption) will be reported.

Subject Replacements: Subjects who discontinue the study will not be replaced.

Sample Size: The sample size is based on the sample size needed for the primary and secondary efficacy analyses. For the primary outcome (proportion of participants who have a decrease of at least 3 points in their Irritability Domain Score), thirty-three participants per group are necessary to detect a difference of 40% having a successful decrease in irritability in one group versus 80% in the other, using a chi-square test with a power of 90% and an alpha of 0.05. This is the effect size we observed in our prior amantadine single-site study.⁴³ For the secondary outcomes, the sample size for the Wilcoxon rank sum test was calculated using the formulas derived by Noether.¹⁶⁷ Thirty-three people are needed in each group to ensure a power of 80%, with an alpha of 0.05, and $p = \text{probability}(Y > X) = 0.70$, where Y and X are random samples from the two populations (groups). Under the null hypothesis $p = 0.50$. To allow for a 10% loss-to-follow up, 37 participants will be enrolled into each of the 2 study arms for a total sample of 74.

Available Sample and Back-up Plan to Achieve Recruitment Numbers: Based on several assessments, we expect to recruit according to our timeline as we have in our prior studies. The PI has successfully conducted several similar pharmacologic studies for irritability in this population which have run according to timeline and provided insight to recruitment obstacles and solutions. In two similar single-site studies, the PI was able to enroll 76 participants over 3.5 years with only a 5% drop out rate. A similar study is near completion at IU with enrollment progressing ahead of schedule. We have ample access to the target population to satisfactorily recruit. Recruitment reports are reviewed by the research team monthly and compared to benchmarks. If/when recruitment falls below benchmark, an action plan will be implemented. If recruitment lags behind benchmarks, we will repeat our intense local advertisement efforts (to both clinicians and persons with brain injury), expand the advertisement to nearby communities, expand our recruitment across Indiana, and provide targeted education about our study and irritability in general to clinicians and persons with brain injury across the state. If necessary, we can extend involvement in this study to other PM&R specialists and psychologists in the region or to nearby residential facilities. If for some reason we still lack adequate recruitment, we will discuss potential options with our NIDRR project officer, such as contracting with another center.

Subject participation duration: 131 days (including open-label); **Study Duration:** 5 years.

Efficacy Analyses:

Hypothesis 1a: Among individuals with TBI of >6 months duration and moderate-to-severe irritability, BUSP compared to placebo will result in a statistically significant greater proportion of responders as defined by a decrease of at least 3 points on the observer-rated Neuropsychiatric Inventory (NPI) Irritability domain scores from baseline to Day 91.

Hypothesis 1b: Among individuals with TBI of >6 months duration, BUSP will result in statistically significant improvement in scores of one or more of the following measures compared to placebo: a) observer and participant ratings of NPI and NPI-Distress Irritability domain scores, b) observer and participant ratings of NPI and NPI-Distress Aggression domain scores, c) participant ratings of TBI-QOL Anger bank, d) observer ratings of SASNOS, e) observer and participant ratings of Global Impression of Change, f) physician ratings of Clinical Global Impressions.

The primary analysis will be intention-to-treat. For Hypothesis 1a, the primary outcome, the percent of participants who are considered to have meaningful reduction in irritability (decrease of at least 3 points in the NPI Irritability Domain Score) from baseline to 91 days, will be compared between the two groups (those receiving active drug and

placebo) using a chi-square test. A logistic regression model will be used to adjust for depression and possible demographic and baseline differences between the two groups and a post-hoc secondary analysis will examine the factors (including depression and anxiety) influencing the effect of BUSP on the primary outcome by including group interaction in the logistic model. For Hypothesis 1b, the change in the observer-rated NPI Irritability Domain Score from baseline to 91 days will be compared between the two groups using a Wilcoxon rank sum (Mann-Whitney) test for ordered categories. The secondary outcomes will also be compared between the two groups using Wilcoxon rank sum tests. For the secondary outcomes, Hochberg's step-up Bonferroni method will be used to control for multiple testing. Secondary analyses will include repeating the analyses above using the PPS population. Wilcoxon rank sum tests will also be performed for separate subgroups such as females, males, participants with injury caused by motor vehicle crashes or falls to test whether BUSP can be efficacious for these separate subgroups. In addition, if a substantial number of participants have depression, a preliminary analysis of the effect of BUSP on PHQ-9 may be performed. The effect of BUSP on GAD-7 will also be performed.

Safety Analysis: Hypothesis 2: BUSP will be tolerated as measured by number and types of the adverse events in the treatment group compared to the placebo group.

